12.6 Record Retention

Clinical records for all participants, including CRFs, all source documentation (containing evidence to study eligibility, history and physical findings, laboratory data, results of consultations, *etc.*), as well as IRB records and other regulatory documentation will be retained by the Investigator in a secure storage facility in compliance with Health Insurance Portability and Accountability Act (HIPAA), Office of Human Research Protections (OHRP), Food and Drug Administration (FDA) regulations and guidances, and NCI/DCP requirements, unless the standard at the site is more stringent. The records for all studies performed under an IND will be maintained, at a minimum, for two years after the approval of a New Drug Application (NDA). For NCI/DCP, records will be retained for at least three years after the completion of the research. NCI will be notified prior to the planned destruction of any materials. The records should be accessible for inspection and copying by authorized persons of the Food and Drug Administration. If the study is done outside of the United States, applicable regulatory requirements for the specific country participating in the study also apply.

12.7 Cooperative Research and Development Agreement (CRADA)/Clinical Trials Agreement (CTA)

Not Applicable

13. STATISTICAL CONSIDERATIONS

13.1 Study Design/Description

We aim to enroll 24 ER+ participants and 12 ER- participants for a total of 36 participants. We plan to “pilot” the 240 mg dose in 5 initial participants with planned assessment of Cmax (Tmax usually at 2 hours) at 2 hours post initial dose (see section 2.3 for further information). In the original 9cUAB30 Phase I study, we saw a flattening of the otherwise linear PK concentration curve; there was a mean Cmax of 957 ng/ml (SD 611) at the 240 mg dose level, similar to the mean Cmax of 983 (SD 434) for the 160 mg dose level. If Cmax had continued to be linear, we will have expected to see a Cmax of 1668 at the 240 mg dose level (calculated using linear regression with a forced intercept of 0, omitting the 240 mg level). We will test the hypothesis H_0 : Cmax=957 (concentration curve is flat) vs the hypothesis H_A :Cmax=1668 (concentration curve is linear) with a one-tailed one-sample Student t-test. Assuming a standard deviation of 611, we will have 0.69 power to reject H_0 : Cmax=957 given that the true mean Cmax is 1668 using a one-tailed one-sample t-test of level 0.05. Based on the results of this analysis, if we do not reject H_0 and the dose gets changed to 160 mg after enrolling 5 participants, 36 additional participants will be enrolled to meet total of 36 participants for data analysis on 160 mg dose and 41 participants total in the study. If we reject H_0 we

will continue at 240 mg/day and enroll 31 more subjects.

This is a single arm open label pre-surgical “window trial” of the novel rexinoid 9cUAB30. The primary objective is to evaluate whether therapy with 9cUAB30 substantially reduces proliferation in breast cancer cells. To test the hypothesis that proliferation decreases in 9cUAB30 treated cases, we plan to examine Ki67 from newly diagnosed breast cancer patients. For each enrolled participant, we will obtain baseline core biopsy tissue samples and post-treatment definitive surgical tissue samples. To account for potential confounding variability associated within the tumor as a result of core biopsy, we plan to include a matched historical nonrandomized “control” group which will have an initial sample as well as post-surgical sample. This matched group will come from archived tissue samples of core biopsy and definitive surgical tissue samples available at each participating Institution. The primary endpoint will be the absolute change in Ki67 expression in each treated participant and matched “control” pair.

The primary analysis will compare the difference in absolute change in Ki67 between treatment and matched “control” group using a one-tailed paired t-test or Wilcoxon signed-rank test, as appropriate, at a significance level of 0.05. We chose the one-tailed test as we are only interested in detecting the reduction in Ki67 expression level with 9cUAB30 as compared to controls.

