1.2 Secondary Objectives

1.2.1 Determine if 14-28 days of oral RXR-selective 9cUAB30 treatment increases apoptotic index, as measured by cleaved caspase 3 assay.

1.2.2 Examine the differences in gene expression from baseline to post-exposure breast cancer samples using a custom gene panel from Nanostring Technologies. Examined genes will be selected as described below and will include up to 48 genes. Prospective biomarkers on the panel will include but are not limited to (A) biomarkers associated with cell proliferation or apoptosis: PCNA, p21, p27, TUNEL assay, caspase 3; (B) potential biomarkers of rexinoid activity reported in published studies: ABCA1, ABCG1, RAR β , SREBP-1c, cyclin D1, IGFBP6; (C) potential biomarkers of response to 9cUAB30 as defined in our preliminary studies: RET, MEN1, mTOR, AKT1, AKT2, 4EBP1, eIF4G1, S6K, IGFBP5, TGF β R1, PPAR α , PPAR γ (D) housekeeping genes for normalization: GAPDH, TUBB, PGK1, GUSB, and CLTC. Additionally, as possible, we will perform IHC for a subset of 5 of the most differentially regulated genes found on Nanostring to verify that gene expression data also results in protein differences.

1.2.3 To examine if the Cmax and safety of 9cUAB30 in the first 5 participants is affected by reducing the number of capsules at the 240mg dose level. That is using 3 capsules of 80mg each instead of 12 capsules of 20mg each.

1.2.4 To examine the Cmax of all participants at baseline and on the day of surgery

1.2.6 Determine if treatment with 2-4 weeks of 9cUAB30 prior to surgery will increase gene expression of type I immune cells in the tumor immune environment of all participants except the first 5

1.2.7 Assess the overall safety of 9cUAB30 in comparison with known retinoid toxicity.

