We initiated a double-blind, placebo-controlled single and multi-dose study of 9cUAB30 in healthy volunteers at 3 participating organizations (UW, UAB, and University of Iowa). Over the course of two different protocols (UWI09-8-02, UWI10-16-01R), 44 participants were enrolled into the study in cohorts of 10 (8 9cUAB30:2 placebo). The starting dose level was 20 mg followed by dose cohorts at 40 mg, 80 mg, 160 mg, and 240mg daily. Subjects received a single, initial dose of study drug (fasting) on day 1 with full pharmacokinetic (PK) and safety monitoring for 24 hours and continued observation off study drug until returning the morning of day 8 for PK sampling and initiation of continuous daily dosing (day 8 -35) when they would return for full PK monitoring for 24 hours after their last dose. Summary PK parameters are presented in Table 1; we observed a linear to near linear increase in peak concentrations and AUC from 20 to 160 mg per day of 9cUAB30. There was no further increase in 9cUAB30 concentrations (Cmax or AUC) from 160 to 240 mg dosing, in fact there was even some evidence to suggest a possible decline in drug levels raising the possibility of absorption issues/interference due to the large number of gelatin capsules at 240 mg (12 capsules). Comparison of baseline and day 36 pharmacokinetics parameters did not suggest drug accumulation or altered metabolism (whether an increase or decrease in absorption or clearance) with repeated dosing.

Table 1: AUC by Dose Level Cohorts 20mg-240mg Multi-day Study (UWI09-8-02, UWI10-16-01R)

Parameter, Time	0 mg (n=10)		20 mg (n=8)		40 mg (n=8)		80 mg (n=8)		160 mg (n=8)		240 mg (n=8)	
Cmax* (ng/ml)												
Day 1	0	(0-0)	128	(41.0-252)	176	(19.8-430)	623	(353-2620)	975	(348-1590)	812	(246-1830)
Day 36	0	(0-0)	122	(54.8-143)	201	(54.5-247)	1060	(220-1690)	1420	(486-5120)	889	(477-1370)

Absolute Change	0	(0-0)	-10.7	(-111-53.7)	-47.8	(-183-185)	492	(-930-751)	950	(-1100-3990)	186	(-1290-623)
AUC*												
Day 1	0	(0-0)	1200	(304-3640)	1570	(181-1900)	5710	(1850-12500)	13000	(2190-62000)	8560	(2000-23400)
Day 36	0	(0-0)	1030	(529-2420)	2280	(865-16000)	8290	(3270-13500)	14400	(10700-40700)	12300	(4990-15400)
Absolute Change	0	(0-0)	-86.3	(-2660-1280)	831	(348-14400)	1730	(-3170-6510)	5820	(-2250-27600)	2710	(-863-7310)

*Data are presented as median (range)

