2.3 Rationale

The goal of this Phase 1b window trial is to ensure that 9cUAB30 produces a biological effect in humans and to identify candidate RXR signaling pathways that may play a role for cancer prevention. We believe the low toxicity of the rexinoid 9cUAB30 will be well-received for prevention of breast cancers in the high risk population, and potentially even better received for women who have had cancer and wish to prevent the occurrence of a second tumor. The results of this study will help to determine the suitability of continued study with 9cUAB30 as a chemoprevention drug in trials proposed by the NCI DCP in the Clinical Development Plan of 9cUAB30.

Treatment with 9cUAB30 in animal models reduced proliferation and number of tumors in both ER+ and ER- breast cancer animal models, suggesting a chemopreventive effect of the drug. To evaluate the anti-proliferative effect in humans, we chose the pre-surgical window trial design. The model of short-term administration of a drug between the window of diagnosis to operative intervention, allows for evaluation of biomarker response from baseline (core biopsy) to post-treatment (surgery). Several pre-surgical trials

have shown the ability of SERMs to reduce proliferation as measured by Ki67 after short-term administration. In these trials administration of tamoxifen or other SERM results in decrease of Ki67 by approximately 40% when surgical resection samples are compared with pretreatment core biopsy samples.³²⁻³⁵ We expect that 9cUAB30 will reduce proliferation and increase apoptosis.

Because breast cancer prevention/therapy preclinical mouse model data with Targretin, 9cRA and 9cUAB30 suggest a linear relationship between increasing dose/concentration and anti-cancer effects, it is important to explore the highest 9cUAB30 dose that pharmacodynamics suggest. The new formulation of 9cUAB30 will significantly lower the gelatin: active ingredient ratio (12 capsules vs 3 capsules) thus raising the potential of higher tissue exposure at 240 mg as compared to 160 mg. Therefore, we plan to “pilot” the 240 mg dose in initial participants with planned assessment of C_{2hr} (Tmax usually at 2 hours) at 2 hours post initial dose. If real time assessment of 9cUAB30 concentrations observe a significant increase over 957 ng/ml levels we will continue at 240 mg/day. If initial concentrations are not appreciably >957 ng/ml with 240 mg/day, participants will be treated at 160 mg/day.

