3. SUMMARY OF STUDY PLAN

Eligible participants will be \geq 18 years of age and newly diagnosed pre- or post-menopausal patients with core biopsy proven invasive breast cancer between 0.5 cm and 5 cm in size or DCIS that is \geq 1.0 cm in size and is either Grade 3 ER+ DCIS or ER- DCIS of any grade

Patients agreeing to participate will take 9cUAB30 240 mg (160 mg contingent on interim analysis) by mouth daily for 14 – 28 days until the time of surgery. Tissue from the core biopsy will be used for the pre-treatment biomarker analysis. The tissue obtained from the surgical excision will be used for post-treatment biomarker analysis. We plan to enroll ER+ participants and ER- participants for a total of up to 41 participants undergoing intervention. We expect the study to be complete within 18-24 months. Beginning in November 2021, participants will be limited only to estrogen receptor negative status.

At baseline all participants will have a complete medical history, physical examination and review of concomitant medications. Participants will undergo laboratory testing to determine eligibility within 30 days prior to day 1 of the study. Baseline laboratory tests will include WBC, differential, hemoglobin,

hematocrit, platelets, INR, PTT, AST, ALT, total bilirubin, alkaline phosphatase, BUN, creatinine, calcium, glucose, albumin, electrolytes (Na, K, Co₂, Cl), HDL, LDL, total cholesterol, triglycerides, thyroid stimulating hormone, FT₃, and FT₄ (may omit any if collected as part of initial cancer workup documented in the medical record within 30 days of study Day 1). A plasma and urine sample for pharmacokinetic (PK) analysis will also be obtained. An additional 30 ml blood sample will be obtained to evaluate and measure the immune response of 9cUAB30 in participants 6-25.

For the first 5 participants, two extra plasma PK samples will be collected after administering the first dose of the study agent at 5 minutes and 2 hours post the drug administration to evaluate the C_{max}. After the first 5 participants complete study participation, their PK samples will be evaluated to determine the C_{max} and adverse events will be evaluated to determine safety of the 240mg dose. Based on this evaluation, it will be determined to continue study dose at 240mg or to reduce to 160mg (refer to section 13.9).

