- b. Once the lab results are obtained to determine eligibility, dispense the study agent in 3 bottles of 30 capsules of 80mg each and administer the first dose of 240mg (3 capsules) at the clinic visit after minimum of 2 hours post their last meal. The participant will be able to eat again after both PK blood draws are performed. This will be considered as Day 1.
- c. Document the date and time in the pill diary and provide the diary to participant with instructions on how to complete.
- d. First post-dose PK sample of 3mL blood will be collected within 5 minutes of drug administration.
- e. Second post-dose PK sample of 3 mL blood will be collected 2 hours from the time the drug was taken. Participants should not eat between the PK blood draws.
- f. The study dose has to be taken in the evening on empty stomach (2 hours after last eating and wait for 1 hour before eating again), every day until the day before surgery.
- g. They will be provided with a BP monitor to measure BP at home. While they are in clinic, they will be instructed on how to use the monitor. The instructions are noted on the BP diary for reference at home (Appendix C). Participants will be asked to measure and document the blood pressure values in the BP diary on Day 7, Day 8 (approximately 24 hours later) and day prior to surgery. All BP measurements should be taken in the morning. They will be instructed to notify the study team if the value of the reading is Systolic \geq 160 or Diastolic \geq 100 (grade 3). The study coordinator will contact the participants on Day 8 by telephone to assess adverse events and other symptoms, review medications and review the BP readings.

For participants 6 onwards:

- a. Review guidelines for agent administration with the participant and provide the diary to participant with instructions on how to complete.
- b. Dispense study agent – 9CUAB30 based on the dose of the study determined by interim analysis. Participant will be given enough study drug for the duration of participation in the treatment phase of the study.
 - Dose 240mg (3 capsules) – dispense 3 bottles of 30 capsules each or

- Dose 160mg (2 capsules) – dispense 2 bottles of 30 capsules each.
- c. Participants may start taking the medication in the evening on the date of dispense, in the evening on empty stomach (2 hours after last eating and wait for 1 hour before eating again) until the day before surgery.

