8.2 Secondary Endpoints

Our secondary endpoint is that treatment with 9cUAB30 for 14-28 days will result in increased apoptosis in breast cancer tissue obtained at surgical resection compared with tissue obtained at diagnostic core biopsy/baseline. Additionally, we plan to explore the effect of 9cUAB30 on a molecular level using Nanostring technology providing further insight into its mechanism of action. Examined genes will include up to 48 genes. Prospective biomarkers on the panel will include but are not limited to (A) biomarkers associated with cell proliferation or apoptosis: PCNA, p21, p27, TUNEL assay, caspase 3; (B) potential biomarkers of retinoid activity reported in published studies: ABCA1, ABCG1, RAR β , SREBP-1c, cyclin D1, IGFBP6; (C) potential biomarkers of response to 9cUAB30 as defined in our preliminary studies: RET, MEN1, mTOR, AKT1, AKT2, 4EBP1, eIF4G1, S6K, IGFBP5, TGF β R1, PPAR α , PPAR γ (D) housekeeping genes for normalization: GAPDH, TUBB, PGK1, GUSB, and CLTC. Additionally, as possible, we will perform IHC for a subset of 5 of the most differentially regulated genes found on Nanostring to verify that gene expression data also results in protein differences.

One of our secondary endpoint will be to examine if Cmax at Day 1 in the first 5 participants is increased from 957ng/ml by reducing the number of capsules for the 240mg dose level. Dose of each capsule has been changed from 20mg per capsule to 80 mg per capsule. We will examine if there is any difference in absorption of the study agent with this formulation. Additionally, we will examine adverse events in these participants for safety due to the change in formulation.

In all of the participants we will examine the urine and plasma drug concentration levels of 9cUAB30 at baseline and on the day of surgery.

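### The Day 1 Cmax in the first 5 participants is in practice a 2-hour concentration, but it is tested against and powered on Phase I Cmax values, so the stated 0.69 power is an upper limit

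*Combined protocol and SAP*

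**What the plan says.** Section 13.1 sets out a one-tailed one-sample t-test at level 0.05 in the first 5 participants at 240 mg. The null mean is 957 ng/mL, the alternative 1668 and the SD 611, and the stated power is 0.69. The measurement is "planned assessment of Cmax (Tmax usually at 2 hours) at 2 hours post initial dose". Section 2.3 describes the same measurement under another name: "with planned assessment of C_{2hr} (Tmax usually at 2 hours) at 2 hours post initial dose".

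Sampling is fixed in section 3, where "two extra plasma PK samples will be collected after administering the first dose of the study agent at 5 minutes and 2 hours" after dosing, and again in section 7.2.1: "Second post-dose PK sample of 3 mL blood will be collected 2 hours from the time the drug was taken". No later Day 1 sample is scheduled.

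Elsewhere the quantity is called Cmax. Objective 1.2.3 asks whether Cmax changes when "using 3 capsules of 80mg each instead of 12 capsules of 20mg each". Section 8.2 will "examine if Cmax at Day 1 in the first 5 participants is increased from 957ng/ml by reducing the number of capsules", and 13.5 repeats this. The Schema and 13.9 lower the dose to 160 mg if Cmax (in 13.9, its mean) does not exceed 957.

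According to 13.1, 957 (SD 611) is the mean Phase I Cmax at 240 mg, and 1668 is a zero-intercept linear projection of Phase I Cmax from the lower doses. Section 2.2.4 says that the multi-dose Phase I subjects received an "initial dose of study drug (fasting) on day 1 with full pharmacokinetic (PK) and safety monitoring for 24 hours".

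**The concern.** The trial takes one informative time point after the first dose, because a 5-minute sample after an oral capsule will not catch the peak. The benchmark is a peak taken from a full profile. The only reason given for equating the two is that Tmax is usually at 2 hours. The human Tmax values in the protocol are 2-3 h (2.2.4) and 2.2-3.1 h (6.2), both from single doses of 5-20 mg. None is given for 160 or 240 mg, or for the 80 mg capsule.

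Within a participant the direction is certain: C2h is at most Cmax. This measurement choice therefore works only against 240 mg. The value is the pharmacokinetic half of the choice between 240 and 160 mg for the rest of the trial, and it is also the test for objective 1.2.3. Under 13.1, failing to reject the null moves the study to 160 mg and means 36 further participants instead of 31.

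**Working it through.** **Inputs from 13.1.** n = 5, null 957, alternative 1668, SD 611, one-tailed t-test at 0.05.

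**Reproducing the stated power.** The noncentrality is (1668 - 957)/611 × √5 = 2.602, and the critical value is t(0.95, 4 df) = 2.132. The noncentral t gives power 0.689, which matches 0.69. This sets the mean of the sampled quantity to 1668. Because C2h cannot exceed Cmax in anyone, the two means agree only if the two values agree in every participant.

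**Allowing a shortfall.** Let r be mean C2h divided by mean Cmax. The documents do not give r, so the values below are assumptions. The tested mean becomes 1668r, still against 957. The SD is either held at 611 or scaled to 611r. For r = 0.90 the tested mean is 1501.2. The noncentrality is then (1501.2 - 957)/611 × √5 = 1.992, or 2.213 with the SD scaled. For the type I error the true Cmax is 957, so the tested mean is 957r. The last two columns show the 13.9 rule, P(mean of 5 > 957), by a normal approximation with standard error 611/√5 = 273.2.

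| r | 13.1 power at true Cmax 1668 (SD 611; SD scaled) | 13.1 type I error (SD 611) | 13.9 keeps 240 mg, true 1668 (SD 611) | 13.9 keeps 240 mg, true 1100 (SD 611) |
|---|---|---|---|---|
| 1.00 | 0.689; 0.689 | 0.050 | 0.995 | 0.70 |
| 0.98 | 0.654; 0.669 | 0.044 | 0.993 | 0.67 |
| 0.95 | 0.599; 0.636 | 0.036 | 0.989 | 0.63 |
| 0.92 | 0.541; 0.599 | 0.030 | 0.983 | 0.58 |
| 0.90 | 0.502; 0.572 | 0.026 | 0.977 | 0.55 |

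For example, at true Cmax 1100 and r = 0.90, (990 - 957)/273.2 = 0.121, which gives 0.55.

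**What r might be.** Assume a one-compartment oral curve with the half-lives in 2.2.4 (2.79, 5.76 and 7.21 h), and solve the absorption rate for a given Tmax. Then C2h/Cmax is 1.00 at Tmax 2.0 h, 0.996-0.997 at 2.2 h, 0.970-0.978 at 2.6 h and 0.921-0.938 at 3.1 h. A participant peaking at 4 h has 0.82-0.85, and one peaking at 1 h has about 0.86-0.93. The half-lives also come from 5-20 mg doses. These figures show how r depends on Tmax; they do not bound it.

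**Side effect of a 2-hour benchmark.** Suppose Cmax is unchanged at 957 but the new capsule moves Tmax from 3.1 h to 2.0 h. The Phase I 2-hour mean would be 957 × 0.938 or 957 × 0.92, while the new mean C2h would be 957. With SD 611, the t-test would reject with probability 0.072 to 0.080 instead of 0.050.

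**The case against.** The 2-hour proxy is disclosed. Section 13.1 gives the sampling time and the reason for it, and 2.3 names the quantity as a 2-hour level and sets its bar at 957. It can be defended as a deliberately demanding bar: a 2-hour level above the old mean peak is stronger evidence of better absorption, and the false-positive rate falls. If Tmax at 240 mg really is about 2 h, nothing is lost. The 2.2-3.1 h figures come from doses no higher than one-twelfth of 240 mg, and the curve used above is an assumption. Under the 13.9 rule a true mean of 1668 is kept almost always. At r = 0.92 the true mean needed to meet 957 moves only to 957/0.92 = 1040, a shift of 83, against a standard error of 611/√8 = 216 for the benchmark itself.

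Most of this stands, and it is why the point is small. Disclosure explains the sampling time, but it does not make the benchmark like-for-like, and the 0.69 is stated without the condition it needs.

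A reader might go further and infer that power is materially below 0.69, that 240 mg is likely to be dropped wrongly, or that 0.92 is the worst case. The documents support none of these. The ratio is unknown and may be close to 1, the 13.9 rule is robust at 1668, and individual peaks at 1 h or 4 h would give lower ratios than 0.92. Nor does the argument fix the net direction of the whole comparison with Phase I: it concerns only C2h against the same participant's Cmax.

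**Conclusion.** The concern holds as a minor one. The tested quantity is C2h, while both the null and the alternative are Cmax figures. The 0.69 is arithmetically right for its inputs. It is an upper limit at a true mean Cmax of 1668 if the SD of C2h is 611 or shrinks in proportion to the mean; an SD that shrank faster than the mean could offset the loss. The power figures for r below 1 are illustrations over assumed ratios, and no lower bound on the ratio can be claimed.

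The effect falls mainly on the 13.1 t-test. For the 13.9 rule it matters only at true means modestly above 957: at 1100, the chance of keeping 240 mg falls from 0.70 to 0.55-0.58 at ratios of 0.90-0.92. The error is conservative for a claim of better absorption and unfavourable to retaining 240 mg. There is also a labelling problem, since 8.2, 13.5 or 13.9 read alone suggests an observed peak.

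**What to change.** Call the quantity C2h wherever it appears: the Schema, objective 1.2.3, section 3, 8.2, 13.1, 13.5 and 13.9. Then:

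- **Interim not yet done, and Phase I Day 1 included a 2-hour sample:** take the null mean and SD at 240 mg and the dose-linear alternative from those 2-hour concentrations, and restate the power.
- **No Phase I 2-hour sample:** keep 957, say that C2h can only fall short of the same participant's Cmax, and present 0.69 as an upper limit.
- **Interim already done:** keep the prespecified test against 957 and add the C2h-to-C2h comparison as a sensitivity analysis for objective 1.2.3.

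The cost is wording changes and a short recalculation from existing data, with no extra draws, visits or participants. The restated power may be less favourable, and the documents do not list the Phase I sampling times. A 2-hour benchmark also cannot separate an earlier Tmax with the 80 mg capsule from a true rise in Cmax, so it gives up some of the present conservatism. The protocol should say so.
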